#### **1.4.3 Drug-related risks and safety measures**

Factors of risk may derive from particular knowledge or the lack thereof, regarding (1) the mode of action, (2) the nature of the target, (3) the relevance of animal models, (4) findings in non-clinical safety studies, and (5) initial clinical experience with BI 474121.

## SAR-CoV-2 related risks

Due to the SARS-CoV-2 pandemic, there is a risk of infection for subjects. The risk to subjects is considered increased based on the need for the study participant to leave his home, and potentially be exposed to people infected with SARS-CoV-2 during transportation to and from the study site, and interactions with people at the facility where the study site is located. This risk may not be necessarily higher than that associated with leaving home for any other reasons (i.e. unrelated to study participation). It is noted that this risk is not exclusive of BI 474121 clinical trials, but rather relevant for any clinical trial requiring in-person visits.

Guidance related to COVID-19 infection and risk assessment for trials with BI 474121 is provided in the IB [[c26859058](#)]. There is no basis to conclude that BI 474121 would likely increase the risk of SARS-CoV-2 infection or progression of COVID-19. For the participants in this trial, it seems unlikely that there will be an additional risk by administration of BI 474121, as these healthy subjects do not belong to the population at higher risk for severe illness from COVID-19. Appropriate risk minimization measures are to be taken in accordance with the public health precautions implemented in the country where the study will be conducted

## Safety measures

The following safety measures will be applied in order to minimize the risk for healthy volunteers:

- Careful dose selection, no dose will be included which has not been previously studied in the FIH study.
- The dose escalation factor is limited to 2.
- Repeated safety laboratory tests will be performed before and during the treatment period (refer to [Flow Chart](#) and see Section [5.2.4](#)). This will also include sensitive serum markers to detect early skeletal muscle injury.
- An ECG monitoring up to Day 5 (96 h post dose) will be performed to cover the anticipated period of highest drug exposure. Continuous ECG measurement will be performed over 4 hours post dose. Dose escalation will be stopped immediately, if at least 2 subjects at one dose level show relevant QT prolongation (see Section [3.3.4.2](#) for details).
- Orthostatic testing will be performed prior to and following study drug administration at the time points indicated in the Flow Chart to assess hemodynamic effects of BI 474121. Dose escalation will be stopped, if clinical symptoms are observed in more than 1 subject (severe) or in more than 3 subjects (moderate) in one dose group.

Proprietary confidential information © 2021 Boehringer Ingelheim International GmbH or one or more of its affiliated companies

- Only if the respective dose of BI 474121 is safe, shows acceptable tolerability, and if no stopping criterion was met (see Section [3.3.4.2](#)), the next higher dose will be given not earlier than 7 days after first dosing of the previous dose group (referring to the 1st subject of each respective dose group). A documented Safety Review must take place prior to each dose escalation (see Section [3.1](#)).
- The subjects will stay at the trial site for at least 48 hours after study drug administration. Based on observed half-life of BI 474121 of ~20 hours in FIH study, this is expected to cover the period of highest risk / peak effect.
- During in-house confinement, the subjects will be under medical observation and thoroughly monitored for both expected and unexpected adverse events.
- SARS-CoV-2 specific test will be conducted at screening visit and within 3 days prior to admission to trial site. Subjects positive in the SARS-CoV-2 test are not eligible to the trial in accordance to exclusion criterion 25 and will be excluded from the trial.
- In case COVID-19 is suspected in a subject during trial participation, a SARS-CoV-2 specific test will be performed immediately. If positive, trial treatment will be discontinued immediately (please refer to section [3.3.4.1](#)) and the subject isolated from other trial participants.

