### 3. DESCRIPTION OF DESIGN AND TRIAL POPULATION

#### 3.1 OVERALL TRIAL DESIGN AND PLAN

This single-rising dose trial is designed as double-blind, randomised, and placebo-controlled within dose groups.

It is planned to include a total of 32 healthy male subjects in the trial. The subjects will be assigned to 4 groups consisting of 8 subjects per group; the groups will be dosed sequentially (see Table 3.1: 1). Within each dose group, 6 subjects will receive BI 474121 and 2 will receive placebo. Only one dose is tested within each dose group.

The dose groups to be evaluated are outlined in Table 3.1: 1 below.

Table 3.1: 1 Dose groups

| Dose Group                   | 1   | 2 | 3  | 4  |
|------------------------------|-----|---|----|----|
| Dose (mg)                    | 2.5 | 5 | 10 | 20 |
| Number of subjects           | 8   | 8 | 8  | 8  |
| Subjects receiving placebo   | 2   | 2 | 2  | 2  |
| Subjects receiving BI 474121 | 6   | 6 | 6  | 6  |

The groups will be dosed consecutively in ascending order, and a time interval of at least 3 days will be maintained between the last drug administration to subjects in the previous dose group and the first drug administration to subjects in the subsequent dose group. Moreover, a time interval of at least 7 days will be maintained between the first drug administration to subjects in the previous dose group and the first drug administration to subjects in the subsequent dose group. The decision to treat the next dose group will be based upon safety and tolerability data of all the preceding dose groups. The next dose group will only be treated if, in the opinion of the investigator, no safety concerns have arisen in the preceding dose groups (i.e. no dose-limiting events occurred), and if none of the pre-specified trial-specific stopping criteria have been met (refer to Section [3.3.4.2](#)).

A documented safety review must take place prior to each dose escalation. Furthermore, an unscheduled safety review meeting can be requested anytime by the Principal Investigator (or an authorised deputy) or the sponsor of the study (for instance, due to the occurrence of any unforeseen adverse events).

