#### **3.3.4.2 Discontinuation of the trial by the sponsor**

Boehringer Ingelheim reserves the right to discontinue the trial at any time for any of the following reasons:

1. Failure to meet expected enrolment goals
2. New toxicological findings, serious adverse events, or any safety information invalidating the earlier positive benefit-risk assessment.
3. Violation of GCP, or the clinical trial protocol (CTP), or the contract with BI impairing the appropriate conduct of the trial.
4. The sponsor decides to discontinue the further development of the investigational product
5. Dose escalation will be stopped if at least 2 subjects on active treatment at one dose level have relevant individual QT prolongations, i.e. a QTc increase of greater than 60 ms from baseline, or absolute QT or QTc greater than 500 ms, as confirmed by a repeat ECG recording
6. Occurrence of severe non-serious adverse events considered as drug-related by the investigator in 2 subjects of the same dose group (8 subjects), or occurrence of at least one drug-related serious adverse event. Moreover, dose escalation will be terminated if more than 3 of the actively dosed subjects at one dose level show drug-related and clinically relevant adverse events of at least moderate intensity.

The investigator / trial site will be reimbursed for reasonable expenses incurred in case of trial termination (except if item 3 applies).

Proprietary confidential information © 2021 Boehringer Ingelheim International GmbH or one or more of its affiliated companies

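### The orthostatic escalation stop in Protocol 1.4.3 is absent from the stopping list in 3.3.4.2, and the visible text does not say whether it is item 6 in short form

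*Protocol*

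**What the plan says.** **Protocol 1.4.3, Safety measures.** The bullet on orthostatic testing sets its own limit on going to a higher dose, which applies "if clinical symptoms are observed in more than 1 subject (severe) or in more than 3 subjects (moderate) in one dose group". It states no condition on causality, clinical relevance or active treatment, and it cites no other section. The bullet just above it, on QT, stops escalation "if at least 2 subjects at one dose level show relevant QT prolongation" and sends the reader to 3.3.4.2 for details. The bullet just below it allows the next dose only when the current dose is safe and acceptably tolerated "and if no stopping criterion was met", again citing 3.3.4.2.

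**Protocol 3.1.** The next group is treated only "if none of the pre-specified trial-specific stopping criteria have been met", with a reference to 3.3.4.2. The same condition applies to dosing each individual within a group.

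**Protocol 3.3.4.2.** The list has six items and none mentions orthostatic testing. Item 5 is the QT rule. Item 6 covers adverse events:

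- Severe limb: severe non-serious events "considered as drug-related by the investigator in 2 subjects of the same dose group (8 subjects"), or at least one drug-related serious event.
- Moderate limb: escalation ends if "more than 3 of the actively dosed subjects at one dose level show drug-related and clinically relevant adverse events" of moderate or greater intensity.

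**Protocol 5.2.3.** Events during orthostatic testing are described as adverse events and graded by intensity.

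**The concern.** A reader of 1.4.3 finds a firm escalation stop tied to orthostatic symptoms. A reader of 3.3.4.2, the section that the escalation decision points to, does not. The closest rule there has the same numbers with different conditions attached, so the same observations can be recorded as criterion met under one section and not met under the other.

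What is at stake is the clarity of a pre-specified safety threshold in healthy subjects, for the haemodynamic effects that 1.4.3 says orthostatic testing is there to assess. The benefit-risk conclusion at the end of 1.4.3 also rests partly on the safety measures listed before it, and this stop is one of them. A measure relied on in that way should be traceable to the list used when escalation is decided.

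**Working it through.** The plan gives no figure to reproduce, so the check sets the two rules side by side and then counts where they part. The group structure (8 subjects, 6 active and 2 placebo) is from Protocol 3.1.

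**Step 1. Compare the conditions.** *In 2 subjects* in item 6 is read as at least 2.

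| | 1.4.3 orthostatic bullet | 3.3.4.2 item 6 |
|---|---|---|
| Event | clinical symptoms | adverse events |
| Severe count | more than 1, i.e. ≥2 | ≥2, non-serious; one drug-related serious event is a separate trigger |
| Severe denominator | dose group (8) | dose group (8) |
| Moderate count | more than 3, i.e. ≥4 | more than 3, i.e. ≥4 |
| Moderate denominator | dose group (8) | actively dosed (6) |
| Causality | none stated | drug-related |
| Clinical relevance | none stated | required in the moderate limb |
| Intensity wording of the moderate limb | moderate | at least moderate |

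The counts agree. The severe limbs share a denominator, so for non-serious events they differ only through causality. The moderate limbs differ in denominator, causality, clinical relevance and intensity wording.

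**Step 2. Isolate the denominator.** Assume moderate symptoms only, all judged drug-related and clinically relevant. Let a = active subjects affected (0 to 6) and p = placebo subjects affected (0 to 2), giving 7 × 3 = 21 patterns.

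- 1.4.3 is met when a + p ≥ 4: 3 patterns at p = 0, 4 at p = 1 and 5 at p = 2, total 12.
- Item 6 is met when a ≥ 4: 3 values of a × 3 values of p = 9.
- The difference is 12 − 9 = 3 patterns: (a, p) = (2,2), (3,1) and (3,2). All three meet 1.4.3 only.
- With p = 0 both rules reduce to a ≥ 4, so there is no difference.
- Item 6 counts other adverse events too. It would also be met if 4 − a further active subjects had another qualifying event: 2, 1 and 1 subjects respectively.

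**Step 3. Causality.** Two subjects with severe symptoms judged unrelated meet 1.4.3 (2 > 1) and do not meet item 6.

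**Step 4. Intensity wording.** Allow moderate and severe symptoms together, all related, clinically relevant and non-serious, and read *moderate* in 1.4.3 as exactly moderate. There are 28 active × 6 placebo = 168 configurations. 1.4.3 is met in 143, item 6 in 139 and both in 138. So 143 − 138 = 5 meet 1.4.3 only, and 139 − 138 = 1 meets item 6 only. That one is 3 moderate plus 1 severe, all active: 3 is not more than 3 and 1 is not more than 1, but 4 active subjects are at least moderate. It arises only on the exactly-moderate reading.

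These are counts of possible patterns, not weighted by likelihood. The documents give no symptom rates, so no probability of a changed decision can be stated.

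**The case against.** The strongest reply is that the bullet is only a summary of item 6. Section 1.4.3 is a benefit-risk overview, the counts match exactly, and 5.2.3 makes orthostatic symptoms adverse events, which brings them within item 6. The QT bullet is shortened in the same way: it leaves out the restriction in item 5 to "at least 2 subjects on active treatment at one dose level have relevant individual QT prolongations" and the requirement "as confirmed by a repeat ECG recording". The sentence before the orthostatic stop also gives the purpose as assessing the drug's haemodynamic effects, which hints at causality. This reply is good, and shorthand is the more likely intention. It does not close the point: the QT bullet carries its cross-reference and the orthostatic bullet does not, and no visible sentence supplies the link.

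A reader might go further and infer that the protocol contains two contradictory rules. The documents do not support that. Both texts are conditions for stopping, item 6 never says escalation must proceed when it is not met, and both can be obeyed by stopping when either is met.

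A reader might also infer that orthostatic effects could go unnoticed at escalation. That is not supported either. Section 3.1 puts orthostatic results in the minimum data set for the Safety Review, and escalation needs the absence of safety concerns in the view of both the Principal Investigator and the Clinical Trial Leader. Under 4.1.5.1 the Clinical Trial Leader is unblinded, so an active-only count is workable.

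Finally, much of 1.2 is blacked out, so the statement that the link is missing applies to the visible text. The absence of an orthostatic item from 3.3.4.2 is not affected, because that list is visible in full.

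**Conclusion.** The point holds as an internal inconsistency of minor to moderate weight. An escalation stop written in 1.4.3 is not in the list that 1.4.3 and 3.1 cite. The nearest listed rule shares its counts but adds conditions, and the visible text does not say whether the two are one rule. A Safety Review working only from 3.3.4.2 would not apply the 1.4.3 wording.

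The textual difference is certain; its effect on decisions is not. The rules part in the moderate-only case only when placebo subjects are also affected, and in the severe case only when symptoms are judged unrelated. The pattern counts rest on the assumptions given with them and should not be read as frequencies. Review of the orthostatic results, and the ability of either decision-maker to block escalation, limit the harm. Those safeguards are matters of judgment, however, and do not settle whether a pre-specified criterion was met.

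**What to change.** Reconcile the orthostatic bullet in Protocol 1.4.3 with 3.3.4.2. The list in 3.3.4.2 should say whether the orthostatic criterion is a separate rule or an instance of item 6. It should state one denominator (whole dose group or actively dosed subjects), one causality condition and one intensity wording (moderate, or at least moderate). Sections 1.4.3 and 3.1 should then refer to that entry, as the QT bullet already does for item 5. Which rule applies is a clinical decision for the sponsor and is not proposed here.

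The cost is a wording amendment to 1.4.3, 3.1 and 3.3.4.2, with no added data, procedures or subjects.

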## **Conclusion**

In summary, BI 474121 has the potential to become an oral treatment for cognitive deficits in patients with schizophrenia and for AD, both indications with a large medical need.

Based upon preclinical data and first clinical data for BI 474121, as well as the implemented safety measures described above, healthy subjects will not be exposed to undue risks in relation to the important information expected from this trial as a basis for further clinical development of this compound.

Healthy volunteers are not expected to have any direct benefit from participation in this trial with BI 474121. Considering the medical need for an effective treatment in schizophrenia and AD, the sponsor considers that the benefit outweighs the potential risks and justifies exposure of healthy human volunteers.

Based on these considerations, the benefit/risk assessment for the administration of BI 474121 to healthy subjects remains unaltered despite the COVID-19 pandemic.

## **2. TRIAL OBJECTIVES AND ENDPOINTS**

### **2.1 MAIN OBJECTIVES, PRIMARY AND SECONDARY ENDPOINTS**

#### **2.1.1 Main objectives**

The main objectives of this trial are to investigate safety, tolerability, and pharmacokinetics (PK) of BI 474121 in healthy Japanese male subjects following oral administration of single rising doses.

[figure not shown]
#### **2.1.2 Primary endpoint**

The primary endpoint for assessment of safety and tolerability of BI 474121 is the percentage (%) of subjects with drug-related adverse events.

#### **2.1.3 Secondary endpoint**

The following pharmacokinetic parameters will be determined if feasible:

[figure not shown]
- $AUC_{0-\infty}$  (area under the concentration-time curve of the analyte in plasma over the time interval from 0 extrapolated to infinity)
- $C_{\max}$  (maximum measured concentration of the analyte in plasma)

[figure not shown]
#### **2.2.2.1 Further Safety and tolerability endpoints**

Safety and tolerability of BI 474121 will be assessed based on:

- AEs (including clinically relevant findings from the physical examination)
- Safety laboratory tests
- 12-lead ECG
- Continuous ECG monitoring
- Vital signs (blood pressure, pulse rate, orthostatic test)

Proprietary confidential information © 2021 Boehringer Ingelheim International GmbH or one or more of its affiliated companies

### 3. DESCRIPTION OF DESIGN AND TRIAL POPULATION

#### 3.1 OVERALL TRIAL DESIGN AND PLAN

This single-rising dose trial is designed as double-blind, randomised, and placebo-controlled within dose groups.

It is planned to include a total of 32 healthy male subjects in the trial. The subjects will be assigned to 4 groups consisting of 8 subjects per group; the groups will be dosed sequentially (see Table 3.1: 1). Within each dose group, 6 subjects will receive BI 474121 and 2 will receive placebo. Only one dose is tested within each dose group.

The dose groups to be evaluated are outlined in Table 3.1: 1 below.

Table 3.1: 1 Dose groups

| Dose Group                   | 1   | 2 | 3  | 4  |
|------------------------------|-----|---|----|----|
| Dose (mg)                    | 2.5 | 5 | 10 | 20 |
| Number of subjects           | 8   | 8 | 8  | 8  |
| Subjects receiving placebo   | 2   | 2 | 2  | 2  |
| Subjects receiving BI 474121 | 6   | 6 | 6  | 6  |

The groups will be dosed consecutively in ascending order, and a time interval of at least 3 days will be maintained between the last drug administration to subjects in the previous dose group and the first drug administration to subjects in the subsequent dose group. Moreover, a time interval of at least 7 days will be maintained between the first drug administration to subjects in the previous dose group and the first drug administration to subjects in the subsequent dose group. The decision to treat the next dose group will be based upon safety and tolerability data of all the preceding dose groups. The next dose group will only be treated if, in the opinion of the investigator, no safety concerns have arisen in the preceding dose groups (i.e. no dose-limiting events occurred), and if none of the pre-specified trial-specific stopping criteria have been met (refer to Section [3.3.4.2](#)).

A documented safety review must take place prior to each dose escalation. Furthermore, an unscheduled safety review meeting can be requested anytime by the Principal Investigator (or an authorised deputy) or the sponsor of the study (for instance, due to the occurrence of any unforeseen adverse events).

Although no formal Safety Review meeting will take place within a given dose group, safety will be continuously monitored during this trial, and an individual will only be dosed in the absence of any safety concern (i.e. no dose-limiting events occurred) and if none of the pre-specified trial-specific stopping criteria have been met (refer to Section [3.3.4.2](#)).

The minimum data set for review consists of the following:

- AEs in the current and preceding dose groups up to at least 48 h post dosing, including clinically relevant findings from ancillary safety testing listed below (Note:

AEs may be ongoing at the time of Safety Reviews and AE information may be subject to change prior to Database Lock)

- Results from 12-lead ECG and continuous ECG monitoring in the current and preceding dose groups up to at least 48 h post dosing
- Vital signs and results from the orthostatic tests in the current and preceding dose groups up to at least 48 h post dosing
- Clinical laboratory tests in the current and preceding dose groups up to at least 48 h post dosing
- Check of criteria for stopping subject treatment as per Section [3.3.4.1](#)

The decision to escalate the dose will be made jointly by the Principal Investigator (or an authorised deputy) and the Clinical Trial Leader (CTL) (or an authorised deputy) after in-depth analysis of all available safety data, especially SAEs (if occurred), AEs, and out-of-range laboratory results (if considered clinically significant). In addition and depending on the results and findings, suitable experts from the sponsor or external institutions may be consulted on an as needed basis. In these cases expert recommendations will be documented in the minutes of the Safety Review and considered for the decision making. Dose escalation will only be permitted if no safety concerns exist neither in the opinion of the Principal Investigator (or an authorised deputy) nor in the opinion of the CTL (or an authorised deputy).

Safety Reviews can be conducted face-to-face or by video/telephone conference. The CTL is responsible for the organisation and minutes of the reviews. Minutes will be signed off by the Principal Investigator (or an authorised deputy) and CTL (or an authorised deputy), and will be filed in the investigator site file (ISF) and trial master file (TMF).

An overview of all relevant trial activities is provided in the [Flow Chart](#). For visit schedules and details of trial procedures at selected visits, refer to Sections [6.1](#) and [6.2](#), respectively.

### **3.2 DISCUSSION OF TRIAL DESIGN, INCLUDING THE CHOICE OF CONTROL GROUP**

For single-rising dose trials, the sequential rising dose design described in Section [3.1](#) is viewed favourably under the provision not to expose the subjects involved to undue risks.

Double-blind conditions regarding the subject's treatment (active or placebo) are maintained within each dose group. However, subjects and investigators will be aware of the dose of drug administered. The disadvantage of the trial design is a possible observer bias with regard to the dose-dependent effects; in addition, the sequential dosing of groups could potentially result in time-related effects. However, as such effects are expected to be small relative to the differences between the doses in the broad range investigated, unbiased comparisons between treatments can still be expected.

It is standard in single or multiple rising dose trials involving healthy volunteers to include a placebo group to control for safety and tolerability of the trial medication. Each dose group consists of 8 subjects, with 6 on active treatment, and 2 on placebo. For data analysis purposes, the placebo control group will include all subjects of all dose groups treated with

Proprietary confidential information © 2021 Boehringer Ingelheim International GmbH or one or more of its affiliated companies

placebo. Six subjects per active treatment group are generally considered to be sufficient for the exploratory evaluation of pharmacokinetics.

